### 8.5.3 COVARIATES AND SUBGROUP ANALYSES

The purpose of performing the covariates and subgroup analyses are to evaluate the possible effects of these covariates on the primary effectiveness endpoints. The intention of these analyses is not for claiming treatment effect on any subgroups. The following covariates will be evaluated based on the imputation for the missing data used for the primary analyses:

- Age group (based on observed quartiles)
- Gender (male and female)
- Race (White and non-White)
- Ethnicity (Hispanic-Latino and not Hispanic-Latino)
- Study site
- MRSE at Postop Week 3 ( $\leq -3.00$  D,  $> -3.00$  D to  $-2.00$  D,  $> -2.00$  D to  $-1.00$  D,  $> -1.00$  D to  $< 1.00$  D,  $\geq 1.00$  to  $< 2.00$  D,  $\geq 2.00$  to  $< 3.00$  D, and  $\geq 3.00$  D)
- MRCYL at Postop Week 3 ( $< 0.50$  D,  $\geq 0.50$  D to  $< 1.00$  D,  $\geq 1.00$  to  $< 2.00$  D,  $\geq 2.00$  to  $< 3.00$  D, and  $\geq 3.00$  D)
- DEQ at Postop Week 3 (0.00 D to  $< 1.00$  D,  $\geq 1.00$  to  $< 2.00$  D,  $\geq 2.00$  to  $< 3.00$  D, and  $\geq 3.00$  D)

For the first co-primary effectiveness endpoint, the difference in monocular DOF at Postop Month 6 between the two lens groups will be derived for each level of each covariate. Additionally, DOF and the difference in DOF between the two lens groups will be stratified by the photopic pupil size ( $< 3.0$  mm,  $\geq 3.0$  to  $\leq 4.0$  mm, and  $> 4.0$  mm) measured at Postop Month 6. Meanwhile, the analysis will be performed by the axial length measured preoperatively ( $< 21.0$  mm, 21.0 mm to  $\leq 26.0$  mm, and  $> 26.0$  mm).

For the continuous effectiveness endpoints (the second and fourth co-primary effectiveness endpoints and the first and fifth secondary effectiveness endpoints), the mean, SD, 95% confidence interval of the mean, median, maximum, and minimum will be calculated by lens group for each level of each covariate. For each covariate, the mean differences among different levels of the covariate will be compared based on two-way analysis of variance (ANOVA) with lens group, covariate, and interaction of lens group and covariate as the

factors. A p-value of 0.15 will be used for evaluating the possible covariate and interaction effects.

For the third secondary effectiveness endpoints, the responder rate along with the exact 95% confidence intervals based on binomial distribution will be provided for each level of each covariate by the lens group. For each covariate, the difference in the responder rate between the two lens groups among the different levels of the covariate will be compared based on the Gail-Simon test. A p-value of 0.15 will be used for evaluating the possible covariate effects.

For the third co-primary effectiveness endpoint and the second and four secondary effectiveness endpoint, the responder rate along with the exact 95% confidence intervals based on binomial distribution will be provided for each level of each covariate based on the primary eyes of the FAS LAL subjects. For each covariate, the responder rate differences among different levels of the covariate will be compared based on Fisher's exact test. A p-value of 0.15 will be used for evaluating the possible covariate effects.

It should be noted that the subgroups of these covariates will be re-examined and may be re-categorized or eliminated due to small sample size (if there are < 10 subjects within each subgroup).

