## 8.5 EFFECTIVENESS ANALYSES

The primary analyses for the primary effectiveness endpoints will be based on the FAS population described in Section 8.3.3. For each type of visual acuity for eyes with study lens exchange or explants before Postop Month-6, the worst observed Month-6 visual acuity of the corresponding lens group will be used to impute the Month-6 visual acuity whether or not the Month-6 data is available.

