### 8.5.1 PRIMARY ANALYSES FOR THE EFFECTIVENESS ENDPOINTS

For the primary analyses of the primary and secondary effectiveness endpoints, the missing Postop Month-6 visual acuity will be imputed by the worst observed Month-6 visual acuity of the corresponding lens group.

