#### **First Co-Primary Effectiveness Endpoint**

From the depth of focus test, the mean logMAR visual acuity of the primary eyes will be calculated and plotted against the corresponding lens diopter of the defocusing lens (defocus curve) at Postop Month 6 for the LAL and Control groups, separately. In case of missing visual acuity values from the depth of focus test, the worst observed visual acuity value of the corresponding defocusing lens diopter at Postop Month 6 of the same lens group will be used to impute the missing visual acuity values at Postop Month 6. A horizontal line at a Y-axis value of logMAR 0.20 will be included in the defocus curves. The lens diopter values corresponding to the intercepted point of the 0.20 logMAR horizontal line and the defocus curve for the negative diopter value will be estimated. The DOF at Postop Month 6 is the absolute difference between the negative lens diopter values corresponding to the 0.20 logMAR visual acuity and 0 diopter. The DOF at Postop Month 6 will be calculated for the two lens groups separately and numerically compared to the target difference value of 0.5 D. No formal statistical comparison will be performed.

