- Subjects who have contracted COVID-19 or feel ill with flu-like symptoms during their participation in the study will not likely be permitted to continue routine scheduled study follow-up, thereby increasing the risk that diagnosis and treatment of potential adverse safety outcomes could be missed or delayed.

RxSight will interact with study sites based on geographic location to determine which sites may be more impacted by COVID-19 during a particular period of enrollment and potentially subject to study disruptions. Sites may be restricted from enrolling in the study for a period of time based on local disease conditions. RxSight will work with sites to ensure that light treatments are continued when possible during any period of study disruptions, while maintaining subject safety.

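### The covariate and site analyses in Section 8.5.3 use worst-value-filled data only: they lose power for real effects and, if follow-up loss is uneven across sites or levels, can flag where eyes were lost

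*Combined protocol and SAP*

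**What the plan says.** Section 8.5.3 lists age group, gender, race, ethnicity, study site and Week 3 MRSE, MRCYL and DEQ, and states: "The following covariates will be evaluated based on the imputation for the missing data used for the primary analyses". Section 8.5.1 defines that imputation: "the missing Postop Month-6 visual acuity will be imputed by the worst observed Month-6 visual acuity of the corresponding lens group". Section 8.5 extends it to eyes with a lens exchange or explant before Month 6, for which "the worst observed Month-6 visual acuity of the corresponding lens group will be used to impute the Month-6 visual acuity whether or not" Month 6 data exist. For depth of focus, the fill is "the worst observed visual acuity value of the corresponding defocusing lens diopter at Postop Month 6 of the same lens group", with no formal test.

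For the continuous endpoints, "the mean differences among different levels of the covariate will be compared based on two-way analysis of variance (ANOVA") with lens group, covariate and their interaction, and "A p-value of 0.15 will be used for evaluating the possible covariate and interaction effects". For the LAL-only responder endpoints, "the responder rate differences among different levels of the covariate will be compared based on Fisher's exact test". The third secondary endpoint uses the Gail-Simon test. The 0.15 threshold applies to all three tests.

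The alternative imputations and tipping-point analysis in Section 8.5.2 repeat the Section 8.5.1 analyses, not those of 8.5.3. Section 8.5.4 uses observed data but is mainly descriptive. Its splits cover Week 3 refractive error, pupil size and axial length, not site, age, gender, race or ethnicity.

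**The concern.** In the LAL–Control comparison, worst-value filling is a choice about conservatism, and this point does not contest it. A covariate question has no conservative direction. The fill gives each missing eye one arm-wide extreme value, whatever its site, age or refraction. Two consequences follow.

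- If eyes are lost evenly across levels, the fill dilutes real covariate differences and inflates the error variance.
- If eyes are lost unevenly, the level with more missing eyes acquires a worse mean, and the test responds to where eyes were lost.

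The same holds for the LAL responder endpoints whenever the worst observed LAL value exceeds 0.20 logMAR, because a filled eye then counts as a non-responder.

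What is at stake is how the covariate and site tables are read. Some unevenness by site is foreseeable: under Section 9.13 the sponsor will work with sites to "determine which sites may be more impacted by COVID-19 during a particular period of enrollment and potentially subject to study disruptions".

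**Working it through.** **Inputs from the documents.** 1:1 allocation; at most 11 sites (Section 4); 100 LAL subjects and 10% drop-out (Section 8.1.2); flag threshold 0.15 (Section 8.5.3). The plan's figure reproduces: 100 / (1 − 0.10) = 111.1, rounded up to 112 per arm, so 224 eyes.

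**Assumptions not in the documents.** Normally distributed acuity; missing shares of about 3% to 10%; the missingness patterns; the effect sizes; LAL responder rates of 60%, 75% and 90%. In the simulations, SDs of 0.10 and 0.15 logMAR gave nearly the same results.

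**Step 1: variance.** Let d be the missing share and z the distance, in SDs, of the arm's worst observed value from its mean. For about 100 normal values, z averages about 2.5. The within-arm SD is multiplied by r = √[(1 − d)(1 + d z²)].
- d = 0.05: √(0.95 × 1.3125) = 1.12
- d = 0.10: √(0.90 × 1.625) = 1.21

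Simulation gives 1.12 and 1.21.

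**Step 2: power with loss unrelated to covariates.** Take a difference of differences of 0.7 SD, with four cells of 56(1 − d) observed eyes and a two-sided critical value of 1.440. On observed data the expected statistic is 0.7 / √(4 / n per cell). Filling shrinks the effect by (1 − d) and inflates the SD by r, so the statistic is multiplied by √(1 − d) / r.
- d = 0.10: observed 0.7 / √(4/50.4) = 2.485, power Φ(1.045) = 85%. Filled 2.485 × 0.784 = 1.949, power Φ(0.509) = 69–70%.
- d = 0.05: observed 0.7 / √(4/53.2) = 2.553, power Φ(1.113) = 87%. Filled 2.553 × 0.873 = 2.228, power Φ(0.789) = 78%.

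Simulation gives 85% to 68% at d = 0.10 (83% to 67% in a second run) and 87% to 75–78% at d = 0.05. A 0.3 SD main effect falls from 73–75% to 57–58% at d = 0.10. The false-flag rate under this even loss stays at 14–16%.

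**Step 3: false flags with uneven loss, two levels of 112 eyes, 3:1 missingness, no true effect.**
- d = 0.10 (15% against 5% missing): shift (0.15 − 0.05) × 2.5 = 0.25 SD. Divided by 1.21 this is 0.207; × √56 = 1.547. Flag rate Φ(1.547 − 1.440) + Φ(−1.547 − 1.440) = 54%.
- d = 0.05 (7.5% against 2.5%): 0.125 / 1.12 = 0.112; × √56 = 0.838. Flag rate 27.4% + 1.1% = 28–29%.

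Simulation gives 53–55% and 27–29%.

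**Step 4: site, 11 sites, no true effect, simulated (1,500 to 3,000 runs per scenario).** Flag rates on filled data:

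| Missingness | Site main effect | Lens-by-site interaction |
|---|---|---|
| Even, 5–10% | 14–16% | 15–16% |
| Mild: 18% in 3 sites, 7% elsewhere (10% overall) | 25–30% | near 15% |
| Mild: 12% in 3 sites, 2.4% elsewhere (5% overall) | 28–30% | near 15% |
| Strong: half of all losses in 2 sites, 10% overall | 55% | 15–16% |
| Strong: 30% in 3 sites, 2.5% elsewhere (10% overall) | 85–87% | 14–16% |
| LAL 30% in 3 sites and 2.5% elsewhere; Control 3% evenly | about 40% | 41–43% |
| LAL about 5% (20% in 2 sites); Control 2% | about 26% | 24% |

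On observed data the rates stay near 15% throughout. The lower end for the first mild pattern comes from a run with sites of equal size. With about 3% missing (6% in 3 sites, 2% elsewhere), the main-effect rate is 19–20%. For a two-level covariate with 3:1 loss that also differs by arm, the interaction rate is 19–20% at 5% missing and 26–28% at 10%.

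**Step 5: Fisher's test, 112 LAL eyes split 56/56, 3:1 loss, 10% missing.** It flags 18–32% on filled data, against 11–13% on observed data. The Gail-Simon test was not simulated.

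**The case against.** **Three stronger readings are tempting, and the documents do not support them.**

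- *The tests will flag whichever sites lost follow-up.* Only if loss is uneven. With even loss the level is nominal.
- *Site-clustered loss would show up as an inconsistent treatment effect.* The largest rates, 85–87%, concern the site main effect: whether mean acuity differs between sites. In the same scenario the lens-by-site interaction stays at 14–16%. A false interaction also needs the uneven loss to differ by arm. The LAL schedule has up to seven more visits than the Control schedule (three adjustments and four lock-ins), so this is possible, but no text establishes it. A site closure would be expected to hit both arms.
- *The trial's conclusions are at risk.* Section 8.5.3 disclaims subgroup claims, and no visible text ties the 0.15 flag to a pooling rule, model change or success criterion. It also states no power target.

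**Other objections carry weight.** The 10% is a planning allowance from the safety sample size, not a forecast of missing Month 6 acuity. The strongest pattern puts 82% of losses (3/11 × 30% = 8.2 of 10.0 points) in three sites. Section 8.3.1 already removes the 17 pre-COVID subjects from the FAS, and Section 9.13 says light treatments will continue where possible.

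Observed-only analysis has its own weakness. The FAS includes attempted but unsuccessful implantations, and Section 7.8.3 exits subjects whose primary eye is not implanted, so dropping missing eyes could hide a real site difference in failures. Filled subgroup tables also reconcile with the primary result.

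These objections limit the size of the point and shape the remedy. They do not supply the missing observed-data check by site, age, gender, race or ethnicity.

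**Conclusion.** The point holds as a minor one. Followed as written, Section 8.5.3 tests covariates on values that carry no covariate information for the missing eyes.

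- **Loss unrelated to covariates:** the level stays near 15%. Power for a 0.7 SD two-level interaction falls from about 85% to 68% at 10% missing, and from about 87% to 75–78% at 5%.
- **Uneven loss:** the site or covariate main effect is falsely flagged at about 25–30% under mild clustering, and at 55–87% under strong clustering with 10% missing.
- **Uneven loss that also differs by arm:** the lens-by-site interaction is falsely flagged at about 24–41%.

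The sizes rest on assumed missing rates, patterns and effect sizes. With few missing eyes the distortion is small. Depth of focus has no test, so its subgroup values may shift but nothing is flagged. The primary LAL–Control conclusions are unaffected.

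**What to change.** In Section 8.5.3:

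1. Run the same covariate, interaction and subgroup analyses on observed Month 6 values alongside the filled-data version.
2. In the observed-data run, keep the Section 8.5 worst-value rule for eyes with lens exchange or explant, and state how eyes with unsuccessful implantation are handled, so that real site differences in failures are not hidden.
3. Tabulate missing eyes by arm at each level of each covariate.
4. State that a covariate or site flag seen only in the filled data will be read as reflecting missingness.

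The cost is a few sentences in the SAP and a second run of the same programs. The downside is a second set of tables whose counts do not add up to the full FAS. The observed-data run also assumes that, within a level, missing eyes resemble observed ones, which is why both versions should be shown.

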#### **8.5.4 ADDITIONAL EFFECTIVENESS ANALYSES**

The following effectiveness outcomes will be summarized descriptively based on the observed data of the implanted eyes or subjects in the FAS. No imputation for missing values will be performed. The 95% confidence interval of the mean, if required, will be calculated based on the t-distribution; the 95% confidence interval of the proportion, if required, will be derived by the binomial distribution. It should also be noted that, for the MRCYL data analyses, the absolute MRCYL value will be used to present the summaries for simplicity.

##### **8.5.4.1 Manifest Cylinder (MRCYL)**

The MRCYL will be summarized by implanted eyes (primary versus fellow eyes) and lens group (LAL versus Control) beginning at the Postop Week 3 visit using descriptive statistics for continuous outcomes (such as mean and standard deviation). The number and percent of eyes with a MRCYL of  $\leq 0.25$  D, 0.50, 0.75 D, 1.0 D, 1.25 D, 1.5 D, 1.75, and  $\geq 2.0$  D at each visit will be reported. The descriptive statistics and percent of eyes with different MRCYL outcomes described previously will be stratified by MRCYL of < 0.50 D,  $\geq 0.50$  to < 1.00 D,  $\geq 1.00$  to < 2.00 D,  $\geq 2.00$  D to < 3.00 D, and  $\geq 3.00$  D at Postop Week 3 in order to compare the findings between the two lens groups.

In addition, the mean manifest cylinder at Postop Month 6 for each lens group and the number and percent of eyes by lens group with increases in cylinder  $\geq 1.00$  D between Postop Week 3 and Postop Month 6 will be reported.

#### 8.5.4.2 Cylinder Correction Accuracy

For eyes measured with  $MRCYL < 0.50$  D at the Postop Week 3 visit, two analyses will be performed. In the primary analysis, the intended cylinder correction will be assumed to be 0 and in a supportive analysis, the intended cylinder correction will be the highest  $MRCYL$  at any of the adjustment visits. For other eyes, the intended cylinder correction will be the  $MRCYL$  measured at the Postop Week 3 visit. The count and percent of eyes with accuracy of cylinder correction to intended target within 0.50 D and 1.00 D will be reported at Postop Month 3 and Postop Month 6 by eye (primary versus fellow) and lens group (LAL versus Control) for the implanted eyes/subjects in the FAS. Additionally, the deviation of the achieved adjustment from the attempted adjustment will be summarized by the descriptive statistics for continuous outcomes. In addition, the descriptive statistics for the LAL eyes with  $\geq 0.50$  D of cylinder at the Postop Week 3 visit will be further stratified into bins approximately 1.0 D in width.

#### 8.5.4.3 Vector Difference

Vector differences between the intended cylinder change and the achieved cylinder change will be calculated and summarized descriptively by eye (primary versus fellow) and lens group (LAL versus Control). In eyes for which no cylinder adjustment is attempted, the intended change will be considered zero and the entire change from Postop Week 3 will be treated as an error.

The analyses will be performed based on the  $MRCYL$  and the cylinder of the aberrometry readings separately.

#### 8.5.4.4 Refractive Cylinder Stability

Refractive cylinder stability will be presented for consistent cohort and eyes with two consecutive visits. The following statistics will be calculated by eye and lens group.

- Percentage of eyes that achieve change of  $\leq 1.00$  D of refractive cylinder;
- Percentage of eyes that achieve change of  $\leq 0.50$  D of refractive cylinder;
- Mean  $MRCYL$  change between two visits and the corresponding 95% confidence interval, mean change per month, and mean change per year

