The LAL must be implanted following specific surgical procedures. If these procedures are not followed by the surgeon, the lens may become scratched or improperly placed in the eye and may need to be explanted prior to light treatments. In order to perform the lens adjustment or the lens lock-in procedures, the subject's pupil needs to be adequately dilated. If this cannot be accomplished for any reason, additional eye drops, injections into the eye, or surgery may need to be utilized to adequately dilate the pupil. If the pupil cannot be adequately dilated after these types of treatments, the LAL may need to be explanted. An unpredicted change in vision can occur resulting from ocular exposure to daylight or any other UV source before the LAL is locked-in. The light treatments may not improve vision and/or manifest refraction, and the adjustment/lock-in procedure may make vision worse, such that it may be necessary to remove and replace the LAL. Vision loss may be permanent and may not be improved by replacing the LAL. There is a potential risk for UV-induced damage to the eye, including the cornea and retina, which may be permanent. UV light can sometimes cause a reactivation of previous herpes virus infection in the eye. A reactivation of herpes virus can cause scarring of the cornea, blurred vision, eye pain, extreme light sensitivity, permanent loss of vision, and possible need for corneal transplant. Temporary or persistent erythropsia and/or temporary or persistent color vision deficiency may occur. Corneal dryness and corneal abrasions from the lens used for adjustment and lock-in can occur. After the lens adjustment(s) or after the lens lock-in procedures, discomfort, itching and light sensitivity may occur. In cases where a spherocylinder adjustment is performed, it is possible that visual disturbances may occur if the IOL rotates or if the correction is not performed on the correct axis of astigmatism.

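### Between-visit cylinder stability is measured by magnitude only, so a shift in manifest axis in an eye with residual cylinder is missed or understated

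*Combined protocol and SAP*

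**What the plan says.** Section 8.5.4.4 states that "Refractive cylinder stability will be presented for consistent cohort and eyes with two consecutive visits". By eye and lens group it gives three statistics. Two have the form "Percentage of eyes that achieve change of" at most 1.00 D or 0.50 D of refractive cylinder. The third is the mean MRCYL "change between two visits and the corresponding 95% confidence interval, mean change per month, and mean change per year". None mentions axis or a vector.

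The preamble of Section 8.5.4 adds that "for the MRCYL data analyses, the absolute MRCYL value will be used to present the summaries for simplicity".

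Vector methods appear in two neighbouring sections. In Section 8.5.4.3, "Vector differences between the intended cylinder change and the achieved cylinder change will be calculated and summarized descriptively", using manifest and aberrometry cylinder separately. Where no cylinder adjustment is attempted, the intended change is zero and all change since Postop Week 3 counts as error. Section 8.5.4.10 pairs Week 3 manifest cylinder with Month 6 autorefraction cylinder.

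Section 9.12 warns that after a spherocylindrical adjustment "it is possible that visual disturbances may occur if the IOL rotates or if the correction is not performed on the correct axis" of astigmatism.

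**The concern.** Cylinder has a size and a direction. If the axis moves between two visits while the size stays the same, the eye's refraction has changed, but a difference of magnitudes records nothing. That eye falls within both limits and adds zero to the mean change.

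The error runs in one direction. Taking magnitudes can hide change but cannot create it, so the percentages within 0.50 D and 1.00 D are at best equal to the vector-based ones and otherwise too high.

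Section 8.5.4.4 is the only visible place where the plan describes how cylinder behaves from one visit to the next. Section 8.5.4.1 counts cylinder increases of at least 1.00 D from Week 3 to Month 6, again by size. Section 8.6.10 covers tilt and decentration. For a lens that may carry an axis-specific correction, readers will look to the stability table for evidence that the correction stays in place, and this table leaves out the axis.

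**Working it through.** **Plan's own figure.** The documents give no target, power or expected value for cylinder stability, so there is nothing to reproduce. The check concerns what the listed statistics can detect.

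**Inputs.** The limits of 0.50 D and 1.00 D come from Section 8.5.4.4. The use of absolute MRCYL comes from the preamble of Section 8.5.4. Preoperative keratometric cylinder below 0.75 D in both eyes comes from Sections 6 and 6.1. The documents give no distribution of postoperative cylinder or axis shift, so the values of C and theta below are assumptions, shown as a range.

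**Direction of the error.** Write the cylinder at each visit as v = (C·cos 2a, C·sin 2a), where C is the magnitude and a the axis. By the triangle inequality, |C2 − C1| ≤ |v2 − v1|. Every eye within a limit by vector is therefore also within it by magnitude, but not the reverse.

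**Pure axis shift.** With C unchanged and the axis moved by theta:

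- magnitude change = 0.00 D
- vector change = 2·C·sin(theta)

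| C (assumed) | 20 degrees | 30 degrees | 90 degrees | Shift that reaches 0.50 D | Shift that reaches 1.00 D |
|---|---|---|---|---|---|
| 0.25 D | 0.17 D | 0.25 D | 0.50 D | 90 degrees | never |
| 0.50 D | 0.34 D | 0.50 D | 1.00 D | 30.0 degrees | 90 degrees |
| 0.75 D | 0.51 D | 0.75 D | 1.50 D | 19.5 degrees | 41.8 degrees |
| 1.00 D | 0.68 D | 1.00 D | 2.00 D | 14.5 degrees | 30.0 degrees |

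For example, 2 × 0.75 × sin 20° = 0.51 D. Section 8.5.4.4 scores every cell in the three shift columns as 0.00 D.

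**Size and axis both change.** The largest possible vector change is C1 + C2. An eye going from 0.50 D to 1.00 D has a magnitude change of 0.50 D and passes the tighter limit, yet its vector change can be as large as 1.50 D. Here the change is understated rather than missed.

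**What the neighbouring vector analyses cover.**

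- Section 8.5.4.3, eyes without cylinder adjustment (including Control eyes): axis change accumulated since Week 3 appears as error.
- Section 8.5.4.3, adjusted LAL eyes: later drift is mixed with the error of the treatment itself.
- Section 8.5.4.10: the two ends of the comparison use different measurements, manifest at Week 3 and autorefraction at Month 6.

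None of these gives the change over one interval between consecutive visits, such as Month 3 to Month 6.

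**The case against.** The strongest reply is that the gap is narrow and that nothing in the trial turns on it. Much of that stands.

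- **Lens rotation.** A reader might infer that rotation of the implanted lens is invisible in this table. That does not follow. If an adjustment has neutralised a cylinder C and the lens then rotates by theta, the residual manifest cylinder is 2·C·sin(theta). For an assumed 0.75 D and 20 degrees it goes from 0.00 D to 0.51 D, and the magnitude table counts that as more than 0.50 D. The blind spot is a shift of the manifest axis in an eye with residual cylinder.
- **Other analyses.** A reader might infer that no planned analysis detects axis drift. Section 8.5.4.3 does detect it since Week 3 in eyes without cylinder adjustment. What is missing is the visit-to-visit interval.
- **Wording.** The two percentage bullets say refractive cylinder, not MRCYL, and the absolute-value rule concerns presentation. It cannot exclude vector use altogether, since Section 8.5.4.3 uses MRCYL in a vector analysis. Magnitude is the natural reading but is partly inferred.
- **Size in this trial.** Eligible eyes have low preoperative keratometric cylinder, and a LAL eye with manifest cylinder of 0.50 D or more after Adjustment #2 goes on to Adjustment #3. In the earlier study in Section 2.1, 96.1% of LAL eyes rotated by 5 degrees or less. Five degrees at an assumed 1.00 D is only 2 × 1.00 × sin 5° = 0.17 D. That study used a prior version of the lens and measured lens rotation, not manifest axis.

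These points limit the size of the problem. They do not remove it: the percentages still cannot fall when only the axis moves.

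**Conclusion.** The point holds in a limited form. Read with the absolute-MRCYL rule, Section 8.5.4.4 measures between-visit stability by magnitude, misses or understates manifest axis shift in eyes with residual cylinder, and gives percentages that can only equal or exceed the vector-based ones.

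The size cannot be estimated from the documents. At 0.25 D of residual cylinder an axis shift alone cannot exceed the 0.50 D limit. At 0.50 D it must be more than 30 degrees, and at 0.75 D about 20 degrees is enough. With low cylinder in most eyes the effect is likely modest. That judgement rests on the eligibility limit, because no postoperative distribution is given.

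A reader might also infer that eyes are being wrongly declared stable. The documents do not support that. Section 8.5.4.4 has no pass or fail criterion, unlike the MRSE rules in Section 8.5.4.8, and cylinder stability is descriptive and not among the visible primary or secondary endpoints. An affected eye is only tallied in a percentage. The change is still worth making because the bias is one-directional and cheap to expose.

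**What to change.** In Section 8.5.4.4 keep the magnitude statistics, say that they are magnitude-only, and add beside them, for each pair of consecutive visits:

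- the vector change per eye from full-cylinder double-angle components, C·cos(2·axis) and C·sin(2·axis)
- the percentage of eyes with vector change within 0.50 D and within 1.00 D
- the mean change in each component with its 95% confidence interval
- all of these overall and in eyes with at least 0.50 D of cylinder at the earlier visit

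The scale must be stated. Conventional J0 and J45 components carry C/2, so for pure rotation their vector length is C·sin(theta), half the full-cylinder value. On that scale 0.75 D at 20 and 30 degrees gives 0.26 D and 0.38 D, and 1.00 D at 15 and 30 degrees gives 0.26 D and 0.50 D. All four would still pass the 0.50 D limit. If J0 and J45 are used, double the vector length before applying the limits. The percentages matter most for individual eyes, since component changes in opposite directions cancel in the mean.

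**Cost.** Some programming, largely shared with Section 8.5.4.3. No new visit or measurement is needed, as manifest refraction is already scheduled at Week 3, Month 3 and Month 6 in both groups. The drawback is that axis noise at low cylinder will lower the percentages slightly: an assumed 10 degree repeat difference at 0.50 D adds 2 × 0.50 × sin 10° = 0.17 D. The separate display for eyes with at least 0.50 D helps the reader judge this.
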